## 1.5 Dose Selection, Benefit/Risk Assessment, and Ethical Review

Results from the phase II study showed that glucose-lowering effect was better when HMS5552 dosage reached 75 to 150 mg/day (75 mg BID). The changes of HbA1c from baseline in different groups were: 75 mg QD, -0.39%; 100 mg QD, -0.65%; 50 mg BID, -0.79%; 75 mg BID, -1.12%. Results showed that the efficacy for 50 mg BID and 75 mg BID groups were significantly better than the placebo group, and the efficacy for 75 mg BID group was significantly better than 75 mg QD and 100 mg QD groups. In general, all dosage groups showed good tolerance. No death, related SAEs or severe AEs were reported. There were no significant differences in AE incidence across groups. No definitive dose-related AEs were reported.

All the safety and PD data above showed that administration of HMS5552 BID was tolerable and had better efficacy. By comparison of 50 mg BID and 75 mg BID groups, the 75 mg BID group showed tolerability and better efficacy meeting clinical needs. Thus, this dosage is expected to have the maximum benefit/risk ratio for patients. Therefore, 75 mg BID was selected for phase III studies.

In summary, based on the data from preclinical and clinical studies, the benefit/risk ratio is good for subjects who received HMS5552. HMS5552 can be used for the proposed phase III studies.

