## 9. Statistical Analysis

### 9.1 Sample Size Determination

This study plans to recruit 450 subjects. Considering possible drop-out of the subjects, a 20% increase of the total subjects, but no more than 564 subjects, will be enrolled. These subjects will be randomized at a ratio of 2:1 into HMS5552 treatment group or control group (placebo), i.e. no more than 376 subjects and 188 subjects are randomized to HMS5552 treatment group and control group.

Based on the planned sample size in efficacy analysis and the randomization ratio (450 subjects, HMS5552 treatment group: control group = 2:1), the study has 91.4% power to detect HMS5552 is superior to the placebo with 0.4% treatment difference (change of HbA1c from baseline at Week 24) under the assumption of type I error (alpha) at 0.05 (two sided) level and within-group standard deviation (SD) for the primary efficacy endpoint as 1.2%.

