### **9.3.4 Safety Analysis**

Descriptive analysis is performed on SS. Safety data are summarized and evaluated for the following two stages: 1) Stage 1: when the subjects completed the double-blind period, and 2) Stage 2: when the whole study is completed.

All AEs are coded using the MedDRA dictionary. The incidences and severity of AEs, and SAEs etc. are summarized and compared between two treatment groups. The detailed description of the treatment emergent SAE and study discontinuation due to AE is listed.

The incidence of hypoglycemic events is compared between treatment groups. The incidence ratio and 95% CI of each treatment group, as well as the incidence difference between treatment groups and its 95% CI are calculated.

The change from baseline of laboratory tests, physical examinations, vital signs, and 12-lead ECG measurements at each visit are summarized. Each index before and after treatment of normal/abnormal changes is also summarized.

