## 5. General Conventions of Statistical Analysis.

Two efficacy and safety statistical analysis will be performed for double-blinding period and the whole treatment period (at most to 52nd week) independently.

For categorical variables, the number and percentage of subjects for each category are calculated. For continuous variables, the descriptive statistics such as sample size (n), mean, standard deviation (SD), median, 1st quartile, 3rd quartile, minimum, and maximum are provided.

Unless otherwise specified, the significant level for between-group comparison is set as 0.05 (two-sided).

Efficacy analysis will be conducted according to the intention-to-treat (ITT) approach. All randomized subjects will be included in the intended treatment group no matter what happens (eg drop-out or treated incorrectly).

Analysis will be summarized by visit (See chapter 6.6 for detailed mapping rules). Data observed in all visits, including scheduled visit, unscheduled and end of treatment visit will be listed and sorted by treatment group, study center, subject ID and visit (if available).

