### 9.3.2. Adverse Events

Adverse events will be coded using MedDRA version 22.0.

Adverse events start before the first exposure to study treatment in double-blind treatment period will be included in the listing of all adverse events.

Treatment emergent adverse events (TEAEs) will be summarized for double-blind period and open-label period respectively. TEAEs are defined as any adverse event present after the first exposure to study treatment or any already presented events that worsened after the first exposure to study treatment.

TEAEs in double-blind treatment period: any adverse event present after the first exposure to study treatment or any already presented events before first double-blind dose administration that worsened after the first exposure to study treatment till the end of double-blind treatment period.

Treatment related adverse events: Adverse events that “Related” or “Probably related” to study treatments.

Important Adverse events: any adverse events, except serious adverse events, leads to results in actions of medical treatment (such as dose discontinuation, dose reducing or symptomatic approach treatment) and abnormal hematological or other lab test results.

Incidence rate of adverse events, treatment related adverse events, serious adverse events and adverse events result in withdrawal from study will be summarized and counted by SOC/PT for each treatment group. The frequency of AEs will be counted for each subject only once per PT name. The difference incidence rate between treatment groups will be compared using Fisher’s Exact test.

Adverse Events will be summarized by severities, if an adverse event occurs more than once on a given subject, then the worst will be counted.

Adverse events with incidence rate  $\geq 2\%$  and  $\geq 5\%$  will be summarized by PT name.

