### 9.3.3. Incidence Rate of Hypoglycemia Events

The number of subjects, percentage, number of events, and exposure adjusted AE incidence rate of subjects with at least one hypoglycemia events will be calculated for each treatment group and will be classified by hypoglycemia (Serious hypoglycemia, fingertip/venous hypoglycemia  $\leq 3.9$  mmol/L, fingertip/venous hypoglycemia  $\leq 3.0$  mmol/L, probably symptomatic hypoglycemia and comparative hypoglycemia)

The percentage, number and exposure adjusted AE incidence rate of subjects with at least one hypoglycemia (fingertip/venous hypoglycemia $\leq 3.9$  mmol/L), hypoglycemia (fingertip/venous hypoglycemia $\leq 3.0$  mmol/L), serious hypoglycemia will be calculated. The number and percentage of the following sub-category will be calculated.

1. Hypoglycemia by severity (Serious hypoglycemia, Non-serious hypoglycemia)
2. Hypoglycemia relationship to study treatment (Related, Not Related)
3. Hypoglycemia with cause (Induced, Non-induced)
4. Hypoglycemia by clinical diagnosis (Symptomatic hypoglycemia, Non-symptomatic hypoglycemia)
5. Time hypoglycemia occurs. (0-4 weeks, 4-8 weeks, 8-16 weeks, 16-24 weeks, 24-28 weeks, 28-34 weeks, 34-40 weeks and 40-52 weeks)

Exposure-adjusted AE incidence rate of subjects =events number / exposure of total population (Year)

Listing of all related information for hypoglycemia events, including duration, starts level, clinical events, severity, category, with or without treatment / intervention, outcome, cause and relationship to study treatment, will be provided.

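### SAP 9.3.3 omits, without logging it, the hypoglycemia confidence intervals and between-group difference that Protocol 9.3.4 requires, and SAP 9.3.2 compares other adverse events by Fisher's test with no effect estimate

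*Supplement*

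**What the plan says.** **Hypoglycemia.** Protocol v1.1, 9.3.4, asks for a 95% CI on the incidence in each group and then states: "as well as the incidence difference between treatment groups and its 95% CI are calculated". (The protocol's term for the per-group figure is an incidence ratio. I read it as the proportion of subjects affected.) SAP 9.3.3 plans, for each glucose category, "The percentage, number and exposure adjusted AE incidence rate of subjects with at least one hypoglycemia", with event counts and several sub-classifications. It names no interval, no difference and no test.

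**Other adverse events.** SAP 9.3.2 summarizes AEs, treatment-related AEs, serious AEs and AEs leading to withdrawal by system organ class and preferred term, and then: "The difference incidence rate between treatment groups will be compared using Fisher’s Exact test". It sets no level of its own, so the general two-sided 0.05 default in SAP section 5 applies.

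**Recording of changes.** Protocol 9.3 says the SAP should document in detail any departure from the protocol's analysis. SAP 2.1, which serves that purpose, has two entries: the wording of the alternative hypothesis and the added exploratory efficacy endpoints.

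**The concern.** Comparing safety between arms at Week 24 is part of the secondary objective (Protocol 2.2, SAP 2.2.1.2). The comparison with placebo is available only in the double-blind period, because placebo subjects then switch to HMS5552. The analysis of that period goes to the regulator (SAP 3.1). Hypoglycemia is a listed safety endpoint and bears on the mechanism: Protocol 1.2 notes that activating glucokinase mutations can cause it. It is therefore the event for which a between-arm estimate is most wanted, and the SAP no longer plans the one the protocol specified.

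For the other AE categories the gap is different. A comparison is planned, but its only output is a p-value. For uncommon events a non-significant p-value says little about how large an excess the data still allow. Protocol 1.5 shows how such results can be read: its summary of phase II tolerability includes "There were no significant differences in AE incidence across groups".

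**Working it through.** **Step 1. Hypoglycemia: the texts side by side.**

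| Output | Protocol 9.3.4 | SAP 9.3.3 | Logged in SAP 2.1 |
|---|---|---|---|
| Incidence per group | yes | yes | – |
| 95% CI per group | yes | no | no |
| Between-group difference | yes | no | no |
| 95% CI of the difference | yes | no | no |

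This part needs no power calculation.

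**Step 2. Reproduce the plan's own figure.** Protocol 9.1 states that "the study has 91.4% power to detect HMS5552 is superior to the placebo with 0.4% treatment difference". Its inputs are 450 subjects at 2:1 (300 and 150), SD 1.2% and two-sided 0.05. The standard error is 1.2 × √(1/300 + 1/150) = 1.2 × 0.1 = 0.12, so the non-centrality is 0.4/0.12 = 3.33. The non-central t with 448 df gives 91.4%, which agrees (normal approximation 91.5%). The documents state no power for safety.

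**Step 3. Power of the Fisher test in SAP 9.3.2.**

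- Arm sizes: 300:150 as planned, and 376:188 at the maximum enrolment of 564 (Protocol 9.1, SAP 2.4). The safety set is everyone randomized and dosed, so drop-outs stay in it.
- Level: two-sided 0.05 (SAP section 5).
- Placebo rates: **assumed**, 1% to 20%, each doubled on HMS5552. The 2% and 5% values match the SAP's reporting cut-offs.
- Formula: power = Σ Σ Bin(x₁; n₁, p₁) · Bin(x₀; n₀, p₀), summed over all (x₁, x₀) with two-sided Fisher p ≤ 0.05.

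| Placebo → HMS5552 | Power, 300:150 | Power, 376:188 |
|---|---|---|
| 1% → 2% | 3.9% | 6.6% |
| 2% → 4% | 14.3% | 19.0% |
| 3% → 6% | 23.2% | 30.6% |
| 4% → 8% | 32.8% | 42.3% |
| 5% → 10% | 42.1% | 52.5% |
| 6% → 12% | 50.7% | 61.5% |
| 10% → 20% | 78.2% | 87.0% |
| 15% → 30% | 94.6% | 98.1% |
| 20% → 40% | 99.2% | 99.8% |

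Power crosses 50% at a placebo rate of about 6% with 300:150, and just under 5% with 376:188.

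**Step 4. What an interval would add** (illustrative counts at 300:150, Newcombe 95% CI for the difference in percentage points).

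| HMS5552 | Placebo | Fisher p | Difference | 95% CI |
|---|---|---|---|---|
| 12/300 (4%) | 3/150 (2%) | 0.40 | +2.0 | −2.1 to +5.1 |
| 30/300 (10%) | 8/150 (5.3%) | 0.107 | +4.7 | −1.0 to +9.4 |
| 60/300 (20%) | 15/150 (10%) | 0.007 | +10.0 | +2.8 to +16.2 |

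In the first two rows the test is non-significant, while the interval shows that an excess of about 5 or 9 points is not ruled out.

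**The case against.** The strongest case on the other side has five parts.

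- **The omission may be an oversight.** The SAP says it is built on protocol chapter 9 and records no decision to remove the hypoglycemia output. Its Table 3 lists a difference from placebo and a 95% CI among the parameters shown in statistical summaries, and the table shells are not in the supplement. It is fair not to call this a deliberate abandonment. But Table 3 sets decimal places and names no safety analysis. Where the SAP wants an interval, as in the efficacy sections, it says so. Someone programming from 9.3.3 would not produce one.
- **For other AEs the protocol promised less.** Protocol 9.3.4 describes a descriptive analysis in which AEs are summarized and compared. Fisher's test with per-arm counts meets that text. This stands: an interval there is an improvement and does not correct an error.
- **A reader might infer that any doubling would usually be missed.** Step 3 does not support this. Doublings of common events are mostly detected, the rates are assumed, and the larger sample is the more relevant one if the drop-out allowance is used. Nor does the power argument apply to hypoglycemia, for which SAP 9.3.3 names no test.
- **A reader might infer that p below 0.05 is the trial's safety decision rule.** No passage says so. The sentence in Protocol 1.5 reports phase II background alongside other tolerability findings.
- **A reader might infer that the report could not show the size of an excess.** Per-arm incidences are reported, so a reader could compute the difference and its interval. The SAP simply does not plan to present them.

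**Conclusion.** The point holds in two parts of unequal weight.

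The firmer part is the hypoglycemia output. The protocol requires per-group intervals and a between-group difference with its interval. SAP 9.3.3 has neither, plans no comparison, and the departure is not logged. This rests on the texts alone.

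The second part is an improvement. The AE categories in SAP 9.3.2 get a p-value without an estimate. For placebo rates below about 5%, a true doubling is more likely than not to be non-significant. For placebo rates of 10% or more, power is at least 78%. The size depends on assumed event rates, independent binomial counts, and a safety set between 300:150 and 376:188.

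Neither part affects the primary efficacy analysis.

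**What to change.** 1. **SAP 9.3.3:** for the double-blind period, restore the hypoglycemia incidence with 95% CI in each group and the between-group difference with 95% CI, for each hypoglycemia category used for assessment. If the sponsor means to leave these out, the change and its reason belong in SAP 2.1.
2. **SAP 9.3.2:** for AEs, related AEs, serious AEs and AEs leading to withdrawal in the double-blind period, add the risk difference (HMS5552 minus placebo) with a 95% CI, naming the method (Newcombe or Miettinen-Nurminen). Label the Fisher p-values descriptive.

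The cost is a short SAP edit and a few extra columns in existing safety tables, with no new data and no extra subjects. Intervals for rare events will be wide.

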### 9.3.3. Incidence Rate of Hypoglycemia Events

The number of subjects, percentage, number of events, and exposure adjusted AE incidence rate of subjects with at least one hypoglycemia events will be calculated for each treatment group and will be classified by hypoglycemia (Serious hypoglycemia, fingertip/venous hypoglycemia  $\leq 3.9$  mmol/L, fingertip/venous hypoglycemia  $\leq 3.0$  mmol/L, probably symptomatic hypoglycemia and comparative hypoglycemia)

The percentage, number and exposure adjusted AE incidence rate of subjects with at least one hypoglycemia (fingertip/venous hypoglycemia $\leq 3.9$  mmol/L), hypoglycemia (fingertip/venous hypoglycemia $\leq 3.0$  mmol/L), serious hypoglycemia will be calculated. The number and percentage of the following sub-category will be calculated.

1. Hypoglycemia by severity (Serious hypoglycemia, Non-serious hypoglycemia)
2. Hypoglycemia relationship to study treatment (Related, Not Related)
3. Hypoglycemia with cause (Induced, Non-induced)
4. Hypoglycemia by clinical diagnosis (Symptomatic hypoglycemia, Non-symptomatic hypoglycemia)
5. Time hypoglycemia occurs. (0-4 weeks, 4-8 weeks, 8-16 weeks, 16-24 weeks, 24-28 weeks, 28-34 weeks, 34-40 weeks and 40-52 weeks)

Exposure-adjusted AE incidence rate of subjects =events number / exposure of total population (Year)

Listing of all related information for hypoglycemia events, including duration, starts level, clinical events, severity, category, with or without treatment / intervention, outcome, cause and relationship to study treatment, will be provided.

#### **9.3.4. Physical Examination**

Normality / abnormality of test results at the end of study treatment will be tabulated. A listing with change from baseline in normality / abnormality at the end of treatment will be provided.

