### 3.1.3 Safety Endpoints

- Adverse events (AEs)
- Hypoglycemia events
- Physical examination abnormality
- Vital signs
- 12-lead electrocardiogram (ECG)
- Clinical laboratory examinations (hematology, blood biochemistry and urinalysis)

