## 7.9 Physical Examination

Full physical examination is conducted at each visit except Visit 2, Visit 3 and Visit 16. The physical examination includes a check on: general appearance, head and neck, chest (heart and lung), abdomen, and limbs.

Any finding from physical examination at subsequent study visits is compared with the results at screening visit and is evaluated for clinical significance. See Section 7.1.3 AEs Related to Examinations and Laboratory Tests for how to record and report AEs related to examinations.

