### **9.3 Statistical Analysis**

After all randomized subjects complete the 24-week double-blind period, the first stage database lock is performed. The study is unblinded for statistical analysis. When all subjects completed the 28-week open-label treatment period, the second database lock and statistical analysis is performed. The details of statistical analysis methods and description are provided in the separate Statistical Analysis Plan. The biostatisticians should formulate the Statistical Analysis Plan according to the clinical study protocol, should record in details the changes that deviate from the planned analysis in the protocol, and refine the final document before database lock and unblinding.

Statistical analysis will be performed using the statistical analysis software SAS version 9.2 or above. The significant level for between-group comparison is set as 0.05 (two-sided).

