#### **9.3.5. Vital Sign**

Change from baseline in all vital signs, height, weight and BMI at each visit will be described. Number, mean, standard deviation, median, minimum, maximum, 1st quantile and 3rd quantile will be calculated.

Change from baseline in weight will be analysed using ANCOVA. The model includes the factors of treatment group, pooled site, interaction of pooled site with treatment group and baseline of corresponding parameters. If the interaction is not significant (2-sided alpha 0.1), then remove the interaction of pooled site with treatment group from model.

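### SAP 9.3.4 cuts the by-arm physical examination table to the end of treatment, where the protocol plans a summary at each visit, and SAP 2.1 does not record the change

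*Supplement*

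**What the plan says.** Protocol v1.1 section 3.1.3 names "Physical examination abnormality" among the safety endpoints, and SAP 2.2.2.4 keeps physical examination on its list. On collection, protocol section 7.9 states: "Full physical examination is conducted at each visit except Visit 2, Visit 3 and Visit 16".

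On analysis, protocol section 9.3.4 states: "The change from baseline of laboratory tests, physical examinations, vital signs, and 12-lead ECG measurements at each visit are summarized". It goes on to ask for a summary of normal/abnormal changes before and after treatment.

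SAP 9.3.4 has two sentences on this endpoint. The first is "Normality / abnormality of test results at the end of study treatment will be tabulated". The second is "A listing with change from baseline in normality / abnormality at the end of treatment will be provided".

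Two further texts bear on this. SAP section 5 gives the general rule "Analysis will be summarized by visit (See chapter 6.6 for detailed mapping rules". Protocol section 9.3 says that the biostatisticians writing the SAP "should record in details the changes that deviate from the planned analysis in the protocol".

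**The concern.** The protocol promises a group-level view of examination findings over the course of treatment. The SAP's section for this endpoint offers a group-level view at one time point. An abnormality that appears on treatment and is gone by the last visit would not enter the table. As worded, the table also shows end status without reference to baseline, so it need not separate a pre-existing abnormality from a new one; that distinction is left to the listing.

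What is at stake is the by-arm summary of one safety endpoint, above all in the randomized double-blind period. There is also a question of procedure. The change is not declared, and a programmer has to choose between the general by-visit rule in section 5 and the narrower wording in 9.3.4. The specific section would normally prevail.

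**Working it through.** The plan gives no figure to reproduce. The check is a comparison of texts and a count of visits.

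**Protocol and SAP compared**

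| Element | Protocol v1.1, 9.3.4 | SAP 9.3.4 |
|---|---|---|
| Timing of the summary | Each visit | End of treatment only |
| Normal/abnormal, before versus after | Summarized | Listing only |

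**Neighbouring SAP sections**

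- Vital signs (9.3.5): "Change from baseline in all vital signs, height, weight and BMI at each visit will be described".
- ECG (9.3.6): a description of normal/abnormal status from baseline to post-treatment.
- Laboratory tests (9.3.7): categorical parameters summarized for each visit.

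Of these four safety sections, only the one on physical examination confines its table to the end of treatment.

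**Is the change logged?** SAP 2.1 has two entries: the removal of one word from the alternative hypothesis, and the addition of other efficacy endpoints. Physical examination does not appear.

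**Count of examinations** (protocol schedule of assessments and section 7.9)

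- Screening and baseline: Visits 1 and 4.
- Double-blind, post-baseline: Visits 5 to 10 (Weeks 4, 8, 12, 16, 20 and 24), which is 6.
- Open-label: Visits 11 to 15 (Weeks 28, 34, 40, 46 and 52), which is 5.
- Total post-baseline: 6 + 5 = 11.

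**Share of examinations in the by-arm table, for a subject who completes treatment**

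- Double-blind analysis, end of treatment at Week 24: 1/6 = 17%, so 6 − 1 = 5 examinations are left out.
- Both planned analyses (SAP 3.1 and 3.2), if each tabulates its own end of treatment (Weeks 24 and 52): 2/11 = 18%, so 11 − 2 = 9 are left out.

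These are shares of examinations, not chances of detecting an abnormality. The latter would need a distribution of onset and duration, which the documents do not give.

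**The case against.** The strongest reply is that little is lost. A reader might infer that transient abnormalities disappear from the safety record, or that only the clinically significant ones survive. The documents do not support that:

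- SAP section 5 promises listings, sorted by treatment group, of data from all visits, and SAP 6.4 repeats that all scheduled and unscheduled values are displayed. Transient findings therefore remain visible subject by subject.
- Protocol section 7.1.3 requires an abnormality to be reported as an adverse event if it points to new or worsened disease or organ toxicity, requires a change in study drug, or calls for further intervention or work-up. Section 7.9 refers to this rule for physical examination. Those events enter the adverse event tables, where SAP 9.3.2 compares incidence between arms with Fisher's exact test.

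A reader might also infer that the randomized comparison is lost because the last examination falls in the open-label period. It is not: SAP 3.1 plans a separate double-blind analysis, with its own end of treatment at Week 24. Early withdrawals are covered too, since SAP 6.6 maps their final safety data to the next scheduled visit.

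Finally, SAP section 4 refers to an attached table shell that is not in the supplement, so the actual layouts cannot be seen.

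All of this limits the consequence; it does not remove the mismatch. A listing is not a between-arm summary, and the adverse event route depends on the investigator's judgement of clinical significance. If the by-visit rule in section 5 is meant to govern, 9.3.4 contradicts it and one of the two needs correcting.

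**Conclusion.** The point holds as an undeclared narrowing of a planned safety summary. The gap is confined to the by-arm table: findings that resolve before the end of treatment are absent from it, while the all-visit listings and, for clinically significant findings, the adverse event tables still hold them. What has no group-level display at all is mainly the transient abnormality judged not clinically significant.

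The counts of 1 in 6 and 2 in 11 rest on two assumptions: that 9.3.4 is followed as written rather than overridden by section 5 or the table shell, and, for the second count, that each planned analysis tabulates its own end of treatment. Severity is minor. The primary analysis is untouched, and nothing in the documents shows that a safety conclusion would change.

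**What to change.** In SAP 9.3.4:

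1. Tabulate normal/abnormal status by arm at each visit where an examination is scheduled, with a shift from baseline. This restores both parts of protocol section 9.3.4 and agrees with SAP section 5.
2. Add the number and percentage of subjects normal at baseline who have any abnormal post-baseline examination, separately for the double-blind and open-label periods. This captures findings that come and go.

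If the sponsor prefers the end-of-treatment display, enter the change and its reason in SAP 2.1 and state in 9.3.4 that it is an exception to the section 5 convention.

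The cost is one or two extra tables. The examinations are already scheduled and recorded, so no new assessment is needed.
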